6.4.4 Descriptive Summary Statistics for Efficacy Parameters

Descriptive statistics of efficacy parameters over time will be presented by treatment. They will include N, arithmetic mean, SD, median, minimum and maximum for continuous parameters and in frequency tabulation form for dichotomous parameters.

6.4.7 Treatment by Center Effect

The randomization in this study is stratified by region (US, LA and EMEA) and by the screening hs-CRP level. Center effect is not considered due to the expectation that many centers will be used and only a small number of subjects will be enrolled in most centers. The region effect will be assessed with respect to the primary efficacy parameter and may be included in the analysis model where appropriate.

6.4.8 Treatment by Baseline Covariate Effect

The treatment-by-baseline effect is not considered; however the baseline will be included in the respective parametric analysis model of the efficacy parameters where appropriate.

6.4.9 Subgroup Analysis

Subgroup analyses may be performed as appropriate upon reviewing the results of the primary analyses.

6.4.10 Handling of Dropouts and Missing Data

For the analyses of dichotomous efficacy parameters by time point, subjects with missing data will not be included in the analysis.

For the analyses of dichotomous efficacy parameters with multiple time points, any missing data will be imputed using the last observation carried forward (LOCF) method except for subjects who withdraw for treatment-related AEs, in which case, any value after the treatment-related withdrawal will be imputed as non-responsive.

For missing data handling in the calculation of ACR20/50/70 responses, because the ACR20 is a composite value, it is sometimes possible to determine it even if there are any missing components. For example, if there is non-responsiveness in at least one of the tender/painful joint count or the swollen joint count, then the ACR20/50/70 is non-responsive. However, if there are missing values in 1 or 2 of the 5 remaining ACR core set components, the method of last observation carried forward (LOCF) will be used to carry forward any of the missing components, and from that mix of actual and carried-forward values, the ACR20/50/70 will be determined. If 3 or more of 5 components are missing, then the corresponding ACR response will not be calculated, and the value of ACR response is considered missing. Missing component at the follow-up visit (Week 16) will not be imputed.

For continuous efficacy parameters, no imputation will be employed.

For the calculation of duration (years) of active RA at Screening, January will be imputed if month of diagnosis is missing.

Other missing data imputation methods may be employed for additional sensitivity analysis if deemed necessary.

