Descriptive statistics of efficacy parameters over time will be presented by treatment. They will include the number of subjects (N), arithmetic mean, standard deviation (SD), median, minimum and maximum for continuous parameters, and in frequency tabulation form for dichotomous parameters.

[REDACTED]

3.8.3.3. *Treatment by Center Effect*

The randomization of this study is stratified by region and by the screening hs-CRP level. Center effect is not considered due to the expectation that many centers will be used and only a small number of subjects will be enrolled in most centers. The region effect will be included in the analysis model where appropriate.

3.8.3.4. *Treatment by Baseline Covariate Effect*

The treatment-by-baseline effect is not considered, however the baseline will be included in the respective parametric analysis model of the efficacy parameters where appropriate.

3.8.3.5. *Subgroup Analysis*

Subgroup analyses may be performed if appropriate.

3.8.3.6. *Handling of Dropouts or Missing Data*

Some efficacy parameters are a composite value derived from a complex instrument. The chance that one of its components is missing increases greatly due to various reasons. In order to minimize missing data, algorithms will be prepared to compute the derived value where reasonable in case some of the components are missing. These algorithms will be described in the SAP.

There will be missing data however, either intermittent like a missing visit or due to subject dropout. For dichotomous efficacy parameters analysis by time point, subjects with missing data will not be included in the analysis. For analysis with multiple time points, any missing data will be imputed using the last observation carried forward (LOCF) method except for subjects who withdraw for reasons related to treatment. In the latter case, any value after withdrawal will be imputed as treatment failure. For parameters analyzed both by time point and with multiple time points, these two approaches would strengthen the findings when they are similar.

For continuous efficacy parameters, no imputation will be employed. This is because the mixed effect model gives valid estimates if the missing data mechanism is “missing at random”, a common assumption made as the first approach for analysis.

Other missing data imputation methods may be employed for additional sensitivity analysis if deemed necessary.

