5.2.2 Secondary Efficacy Parameters

The secondary efficacy parameters (evaluated at Weeks 2, 4, 8, 12, 16 and EOT, respectively, unless otherwise stated):

- Percentage of subjects achieving ACR20/50/70 response rate (except ACR20 at EOT which is the primary parameter)
- Change from baseline in SDAI
- Percentage of subjects who achieved remission based on SDAI (≤ 3.3)
- Percentage of subjects who achieved low disease activity based on SDAI (≤ 11)
- Change from baseline in CDAI
- Percentage of subjects who achieved remission based on CDAI (≤ 2.8)
- Percentage of subjects who achieved low disease activity based on CDAI (≤ 10)
- Percentage of subjects achieving Boolean Remission
- Change from baseline in DAS28-CRP
- Percentage of subjects with DAS28-CRP of <2.6
- Percentage of subjects with DAS28-CRP of <3.2

- Percentage of subjects with good European League Against Rheumatism (EULAR) response at Week 12
- Percentage of subjects with moderate EULAR response at Week 12
- The lowest percentage change from baseline of 3 measures: tender joint count, swollen joint count and median change of the remaining 5 core measures (numeric ACR [ACR-N] index)
- Change from baseline in the Health Assessment Questionnaire Disability Index (HAQ-DI)
- Change from baseline in the number of tender and swollen joint counts (68/66 joints will be counted)
- Change from baseline in subject pain score by numeric rating scale (NRS)
- Change from baseline in subject global assessment (SGA) of disease activity by NRS
- Change from baseline in physician global assessment (PGA) of disease activity by NRS
- Change from baseline in hs-CRP

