6.1 Sample Size

Approximately 250 eligible subjects (50 in each treatment group) are randomized into the DB treatment period of this study.

The primary efficacy evaluation will be to compare the ACR20 response rate between JTE-051 with placebo at EOT. From one study comparing mavrilimumab with placebo in combination with stable MTX, the ACR20 of mavrilimumab and placebo at Week 12 were 0.69 and 0.40, respectively. Assuming the ACR20 of at least one of the JTE-051 doses to be at least 0.30 above placebo, the following sample size per group will be needed to detect a statistical significant difference at the 5% level with about 80% power (using 2-sided Fisher's exact test):

Placebo ACR20	0.25	0.35	0.45
Sample size per group	47	48	47

About 50 randomized subjects per group would therefore give at least an 80% power for a range of placebo responses. The sample size calculation was carried out using the software SiZ 6.2 (Cytel Inc., 2013).

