6.4.3 Supportive Analyses of Efficacy Parameters

For dichotomous efficacy parameter analysis with multiple time points, a supportive analysis will be performed using a generalized estimating equation (GEE) method on the logit scale. The model includes effects for treatment, time, treatment by time interaction, stratification factors and subject as the repeated factor. The odds ratio (OR) of each JTE-051 dose group relative to placebo at the same time point will be estimated.

Model: (generalized estimating equation (GEE) method on the logit scale)

```
proc genmod data=xxxx;
  class usubjid trtn(ref=1) region(ref=0) hscrpn(ref=0);
  model SAEP=trtn time trtn*time regionn hscrpn;
  repeated subject=usubjid/type=un corrw;
run;
```

[figure not shown]
Note: SAPE denotes any dichotomous efficacy parameter, regionn and hscrpn are stratification factors, we can add other stratification when needed.

The supportive efficacy parameters utilizing the non-hs-CRP will be analyzed in a similar manner as their secondary efficacy counterparts using hs-CRP.

All analyses will be performed two-sided at the 5% significance level. No formal multiple comparison adjustment will be made; therefore, results should be interpreted with the multiplicity in mind. The estimated treatment effect (relative to placebo), e.g., odds ratio, from the model, along with a two-sided 95% confidence interval (CI) and p-value, will be tabulated where appropriate. The Newcombe's CI of the rate difference between JTE-051 dose and placebo will be computed when performing the Fisher's exact test. Graphical presentations of the treatment profile will be depicted for the primary and key secondary analyses. Sensitivity analysis and model fit assessment may be conducted, and data transformation may be employed if appropriate.

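### In the supportive multi-visit GEE, the LOCF rule as written lets on-drug responses stand in for missing responses at the off-drug Week 16 visit

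*SAP*

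**What the plan says.** SAP section 5.2.2 lists the secondary parameters, apart from the Week 12 EULAR responses, as "evaluated at Weeks 2, 4, 8, 12, 16 and EOT, respectively". SAP section 3 puts the Follow-up Visit about four weeks after the last dose. Footnote i to SAP Table 1 puts the last dose on the day before Visit 6, so Week 12 is on drug and Week 16 is off drug.

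SAP section 6.4.3 adds a supportive GEE on the logit scale for dichotomous parameters, with an odds ratio against placebo at each time point. It does not list the visits that enter the model.

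SAP section 6.4.10 then gives three rules that bear on Week 16:

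- By-time-point analyses leave out subjects with missing data.
- In multi-visit analyses, "any missing data will be imputed using the last observation carried forward (LOCF) method except for subjects who withdraw for treatment-related AEs"; after such a withdrawal, values are set to non-response.
- Within the paragraph on ACR20/50/70 components: "Missing component at the follow-up visit (Week 16) will not be imputed".

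Protocol section 3.8.3.6 has the same multi-visit LOCF rule, also without a Week 16 exception, but words its withdrawal exception more broadly: "except for subjects who withdraw for reasons related to treatment".

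**The concern.** A subject who responds at Week 12 and then misses the follow-up visit would enter the Week 16 comparison as an off-drug responder, although the response was seen on drug.

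The component sentence suggests that the authors did not want values carried into follow-up, but it does not achieve that. If a Week 16 component is not imputed, the ACR response may be left missing. A missing response is itself missing data under the multi-visit rule, so LOCF can fill it. The sentence also says nothing about the SDAI, CDAI, DAS28 and Boolean endpoints, which are likewise assessed at Week 16. Two programmers could follow the text and produce different Week 16 odds ratios.

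Protocol section 3.8.3.6 says that the by-visit and multi-visit approaches strengthen the findings when they agree. If values are carried across the end of treatment, agreement or disagreement at Week 16 is hard to interpret.

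**Working it through.** **The plan's own figure.** The documents give no figure for Week 16 imputation and no missing-data rate. The nearest design figure is the sample size table in SAP section 6.1, which assumes a 0.30 gain over placebo. Exact enumeration of the two-sided Fisher test gives power 0.799 at each tabulated entry: n=47 for 0.25 vs 0.55, n=48 for 0.35 vs 0.65, and n=47 for 0.45 vs 0.75. The table therefore reproduces. Its middle column supplies the on-drug rates used below.

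**Inputs**

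- Week 12 (on drug): active 0.65, placebo 0.35, taken from 0.35 + 0.30 in the table.
- Week 16 (off drug): active 0.40, placebo 0.33. Assumed.
- Share missing at Week 16, *m*: 10% or 15% in both arms, unrelated to response. Assumed.
- No missing subject is a related-AE withdrawal. Assumed here and relaxed below.

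**Formula.** Week 16 rate under LOCF = (1 − *m*) × off-drug rate + *m* × on-drug rate. The odds ratio is the marginal one, without adjustment for strata and with each visit taken on its own.

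| *m* | Active | Placebo | Difference | Odds ratio |
|---|---|---|---|---|
| 0 | 0.400 | 0.330 | 7.0 points | 1.35 |
| 10% | 0.9 × 0.40 + 0.1 × 0.65 = 0.425 | 0.9 × 0.33 + 0.1 × 0.35 = 0.332 | 9.3 points | 1.49 |
| 15% | 0.85 × 0.40 + 0.15 × 0.65 = 0.4375 | 0.85 × 0.33 + 0.15 × 0.35 = 0.333 | 10.45 points | 1.56 |

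**Varying the fade.** Hold placebo at 0.35 throughout and active at 0.65 on drug.

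| Off-drug active rate | OR without LOCF | OR with LOCF at *m* = 5, 10, 20, 30% |
|---|---|---|
| 0.35 (complete fade) | 1.00 | 1.07, 1.14, 1.29, 1.46 |
| 0.50 (partial fade) | 1.86 | 1.91, 1.97, 2.09, 2.22 |
| 0.65 (no fade) | 3.45 | 3.45 throughout |

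**Varying the reason for missingness.** Let a share *f* of the missing active subjects be related-AE withdrawals, who are scored as non-responders, with none on placebo. On the rates of the first table, the shift in the difference is *m* × [0.65(1 − *f*) − 0.40 − (0.35 − 0.33)] = *m* × [0.65(1 − *f*) − 0.42]. It is zero at *f* = 1 − 0.42/0.65, about 35%. At *f* = 50% the difference is 0.3925 − 0.332 = 6.05 points for *m* = 10%, and 0.38875 − 0.333 = 5.6 points for *m* = 15%. Both are below 7.0.

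**Time in the model.** In the GEE code of SAP section 6.4.3, time is not in the CLASS statement, so each arm gets a straight line on the logit scale. I fitted illustrative rates at Weeks 2, 4, 8, 12 and 16 (active 40/50/60/65/40%, placebo 22/27/32/35/33%) with an independence working model. The fitted Week 12 odds ratio is 2.25, where the input rates give 3.45. With LOCF at 10% missing it is 2.33. The distortion comes from including an off-drug visit in a linear-time model. LOCF slightly reduces it.

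**The case against.** The strongest reply is that little depends on this. The GEE is labelled supportive. The by-visit Fisher and trend tests already analyse Week 16 on observed cases, and the primary endpoint, ACR20 at EOT, does not involve Week 16. The SAP never says outright that the GEE includes Week 16, and the component sentence shows an intention not to impute at follow-up. The visible text states no off-treatment efficacy objective. A 3.5-point shift is also small beside a standard error of about 9.6 points at 50 per arm: √(0.40 × 0.60/50 + 0.33 × 0.67/50) = 0.096.

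All of this stands and limits the importance of the point. It does not settle which rule governs a wholly missing Week 16 response, or any Week 16 response outside the ACR family.

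A reader might infer four stronger things that the documents do not support:

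- **That the Week 16 odds ratio is not an off-treatment estimate at all.** Only subjects missing at Week 16 are affected, so the estimate is a mixture. Early withdrawals are also asked to attend a follow-up visit about four weeks after their last dose (Protocol sections 3.4 and 3.5.3), so not every carried value need be on drug.
- **That LOCF necessarily inflates the active arms.** The direction depends on fade and on the share of related-AE withdrawals.
- **That the protocol requires non-response after withdrawal for lack of efficacy.** Its exception does not define treatment-related reasons, and the withdrawal list in Protocol section 3.4 has no such category. Protocol section 3.8 also allows the SAP to modify the plan.
- **That LOCF at Week 16 distorts the on-treatment estimates through linear time.** The fit above shows that the cause is the inclusion of Week 16 itself.

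**Conclusion.** The concern holds as a gap between two rules in SAP section 6.4.10. As written, and on the natural but inferred reading that the GEE includes Week 16, a missing Week 16 response is filled from an earlier, usually on-drug, visit. The component sentence does not clearly stop this for ACR responses and does not reach the other dichotomous endpoints.

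Under the main assumptions the Week 16 difference is overstated by 2.3 points at 10% missing and about 3.5 at 15%. Those figures rest on assumed fade and missingness and on no related-AE withdrawals among the missing. The shift disappears without fade and changes sign once more than about 35% of missing active subjects are such withdrawals. The consequence is confined to a supportive analysis, but the correction costs almost nothing and should be made.

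Separately, the SAP narrows the protocol's withdrawal exception to adverse events without giving a reason. This affects LOCF at every visit and should be reconciled.

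**What to change.** In SAP sections 6.4.3 and 6.4.10:

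1. State that the GEE and its LOCF use Weeks 2, 4, 8 and 12 only. This also keeps an off-drug visit out of a model that codes time as linear.
2. State that no response is carried into Week 16 for any dichotomous endpoint, and that Week 16 is assessed by the by-visit observed-case analysis already planned.
3. Either restore the protocol's wording of the withdrawal exception, with a definition of which reasons count, or justify limiting it to treatment-related adverse events.

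The cost is a few lines of SAP text. The GEE would give no Week 16 odds ratio, and subjects missing at Week 16 would not contribute at that visit.

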3.4. Removal of Subjects from the Study

[figure not shown]
A subject will not participate further in the study under the following conditions:

1. Withdrawal by Subject: subjects have the right to withdraw from the study at any time. However, if a subject withdraws consent because of experiencing an adverse event, the reason for subject termination should be documented as the adverse event.
2. Adverse Event: a clinical or biological adverse event or intercurrent condition(s), requiring study drug discontinuation, whether or not related to the study drug

If grade 3 findings (defined as severe or medically significant but not immediately life-threatening; hospitalization or prolongation of hospitalization indicated; disabling; limiting self-care activities of daily living [ADL] such as bathing, dressing, undressing, feeding self, using the toilet, taking medication, but not bedridden), according to the CTCAE²⁵, are noted in a subject, he/she must be promptly evaluated by the Investigator (including repeat tests, evaluation of the baseline parameters, concomitant medications, etc.) for potential withdrawal from the study. Every effort should be made to discuss with the study's Medical Monitor prior to final decision, unless not feasible, based on safety considerations. Subjects who interrupted study drug administration due to a grade 3 CTCAE finding may be re-started on therapy if the event has resolved and it is considered appropriate by the Investigator and Sponsor or designee.

Notes:

- The investigator may decide to evaluate or withdraw the subject from the study based on findings of lesser than grade 3 severity, according to his/her judgment.

3. Consistent* Non-compliance with Study Drug (i.e., <80% or >120% compliance; exceptions on a case-by-case basis may be permitted if approved by Sponsor or designee)

*Determined at >1 study visit during the Treatment Period. If compliance of <80% or >120% is identified at a study visit, the Investigator or designee is to counsel the subject and ensure steps are taken to improve compliance.

4. Inclusion/Exclusion Criteria Not Met: the subject was randomized in the study and did not meet all inclusion/exclusion criteria mandated by the protocol (exceptions on a case-by-case basis may be permitted if approved by Sponsor or designee)

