5. Protocol Violation: the subject is non-compliant with regard to this protocol (other than the withdrawal criteria 3. and 4. listed above), as determined by Sponsor or the Investigator
6. Lost to Follow-up
7. Death
8. Study Terminated by Sponsor: the sponsor may suspend or terminate the study or part of the study at any time for any reason
9. Pregnancy
10. Investigator Decision: the Investigator decides a subject should be discontinued for any reasons other than those already mentioned (actual reason must be documented by site)
11. Other: actual reason must be documented by site

Subjects who are removed from the study or withdraw consent to participate in the study after receiving the first dose of study drug on Day 1 will be requested to complete an Early Termination Visit at which time the subject will undergo all the procedures described for Visit 6 (EOT). Every effort should be made to perform the EOT assessments as soon as possible after the decision of discontinuation is made and prior to any changes made in the subject's anti-RA therapy. Additionally, at approximately 4 weeks after study drug discontinuation, subject should return for a Follow-up Visit, where all procedures as described at Visit 7 should be performed.

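### In the supportive multi-visit GEE only, the SAP counts treatment-related AE stops as non-response but lets LOCF carry forward responses for inefficacy stops and unrelated deaths

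*SAP*

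**What the plan says.** Protocol 3.8.3.6 (Handling of Dropouts or Missing Data) uses LOCF for dichotomous endpoints in analyses with multiple time points, "except for subjects who withdraw for reasons related to treatment. In the latter case, any value after withdrawal will be imputed as treatment failure". The protocol does not define which reasons count as related to treatment.

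SAP 6.4.10 keeps the LOCF base: "For the analyses of dichotomous efficacy parameters with multiple time points, any missing data will be imputed using the last observation carried forward (LOCF) method". It restates the exception as "except for subjects who withdraw for treatment-related AEs, in which case, any value after the treatment-related withdrawal will be imputed as non-responsive". No explanation is given for the change.

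For single-visit analyses the SAP has a different rule: "For the analyses of dichotomous efficacy parameters by time point, subjects with missing data will not be included in the analysis".

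Protocol 3.4 lists eleven reasons for removal: withdrawal by subject, adverse event, non-compliance, eligibility not met, protocol violation, lost to follow-up, death, sponsor termination, pregnancy, investigator decision and other. None is lack of efficacy or worsening of RA. A consent withdrawal is redirected to its cause in one case only: "if a subject withdraws consent because of experiencing an adverse event, the reason for subject termination should be documented as the adverse event". The remaining routes are catch-alls, such as "Investigator Decision: the Investigator decides a subject should be discontinued for any reasons other than those already mentioned".

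**The concern.** Two kinds of informative dropout are treated in opposite ways. A subject who leaves because of a drug-related AE is set to non-response at later visits. A subject who leaves because the disease is not controlled keeps the last observed status, which may be a response from an earlier visit. A responder who dies of an event judged unrelated is handled the same way.

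Inefficacy stops would plausibly be more common on placebo and low doses, although the documents give no rates. If so, late-visit response on placebo is raised relative to active. Protocol 3.8.3.6 says that agreement between the by-visit and multi-visit approaches strengthens the findings, so a tilt in one of them weakens that comparison. The disposition table planned in SAP 6.2 also cannot show stops for lack of efficacy as a category, because none is listed.

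**Working it through.** **1. The two rules side by side**

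| Stop, with no later value | Protocol 3.8.3.6 | SAP 6.4.10 |
|---|---|---|
| Treatment-related AE | Failure | Non-response |
| Inefficacy, not recorded as a related AE | Failure on the natural reading; term undefined | LOCF |
| Death from an event judged unrelated | Not named; LOCF on a plain reading | LOCF |
| Other reasons | LOCF | LOCF |

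The SAP's narrowing accounts for the second row. The third row is a gap in both documents.

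**2. Where the rule acts.** SAP 6.4.3 labels the multi-visit GEE supportive. The primary analysis (SAP 6.4 and 6.4.1) takes the last value in the double-blind period whatever the reason for stopping. By-visit Fisher and trend tests omit subjects with missing data. Continuous endpoints are not imputed.

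**3. The plan's own figures.** SAP 6.1 gives 47, 48 and 47 per group for a gain of 0.30 over placebo rates of 0.25, 0.35 and 0.45. Exact enumeration of the two-sided Fisher test gives 79.9% power in each case, and 83.5%, 82.8% and 83.5% at 50 per group. The figures reproduce. This point does not affect them, because they concern the primary test.

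**4. Effect of carrying forward rather than failing inefficacy stops.** Let d be the share of an arm that stops for inefficacy, and s the share of those whose last available value was a response. Carrying forward adds d × s to the arm's late-visit rate. The documents give neither quantity, so all values of d and s are assumptions.

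| d | s = 0 | s = 0.1 | s = 0.2 | s = 0.4 |
|---|---|---|---|---|
| 5% | 0 | 0.5 | 1.0 | 2.0 |
| 10% | 0 | 1.0 | 2.0 | 4.0 |
| 15% | 0 | 1.5 | 3.0 | 6.0 |

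Entries are percentage points. With 50 per arm one subject is 1/50 = 2 points, so 4.0 points is two subjects.

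The treatment difference changes by −(d on placebo − d on active) × s. With 10% on placebo, none on active and s from 0 to 0.4, it shrinks by 0 to 4 points.

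**5. A scenario with stops in both arms (assumed).** Completer response is 0.65 on active and 0.35 on placebo. Related-AE stops are 10% and 2%; inefficacy stops are 4% and 10%.

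- Active, SAP rule: (1 − 0.10 − 0.04) × 0.65 + 0.04s = 0.559 + 0.04s
- Placebo, SAP rule: (1 − 0.02 − 0.10) × 0.35 + 0.10s = 0.308 + 0.10s
- Difference, SAP rule: 0.251 − 0.06s, which is 0.251, 0.245, 0.239 and 0.227 at s = 0, 0.1, 0.2 and 0.4
- Difference with both kinds of stop failed: 0.559 − 0.308 = 0.251 throughout

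The loss is 0 to 2.4 points.

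**The case against.** The strongest reply is that s is probably small. Protocol 3.4 asks every early leaver for an Early Termination Visit with all Visit 6 procedures, promptly and before any change in anti-RA therapy. Someone leaving with uncontrolled disease will then usually have a non-response as the last value, and LOCF and failure agree. This largely stands. It does not close the gap: Protocol 3.4 only requests the visit, Protocol 3.5.2 qualifies it as if possible, and a subject who dies may have none. SAP 6 limits summary tables to scheduled visits, and the SAP does not say how this visit maps to a time point.

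The direction is also conservative for efficacy if inefficacy stops are more common on placebo. That stands too, though the sign would reverse for any dose with more such stops than placebo.

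Protocol 3.8 lets the SAP modify the plan, so a reader who infers a breach of protocol would be wrong. The SAP may simply have made a vague term operational, and treating inefficacy as a treatment-linked reason is a reading, not explicit text.

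A reader might also infer that inefficacy stops cannot be recovered at all. That is too strong: Protocol 3.4 requires the actual reason to be documented for *Investigator Decision* and *Other*. Only *Withdrawal by Subject* has no such general instruction. The eCRF is not among the documents, so its pick-list is unknown.

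**Conclusion.** The point holds for the supportive multi-visit GEE. SAP 6.4.10 narrows the failure rule without a stated reason, the listed withdrawal reasons do not identify inefficacy, and an earlier response can be carried past an inefficacy stop or an unrelated death. The effect is about 0 to 4 percentage points off the treatment difference, against an assumed effect of 30. That range rests on an excess of inefficacy stops on placebo of up to 10 percentage points and on up to 40% of those subjects last showing a response. It is 0 to 2.4 points in the two-arm scenario and near 0 when the Early Termination Visit captures the non-response.

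Two stronger readings are not supported. One is that the primary result is tilted in this way; the primary analysis does not apply the rule. The other is a distortion of 4 to 8 points, reached by adding the responders that a high-dose arm loses when related-AE stops are failed. If 5 of 50 stop in each arm and 20–40% of them had responded, each arm shifts by 1–2 subjects, or 2–4 points. The active-arm half arises under the protocol's rule as well, so the narrowing does not cause it.

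**What to change.** 1. In SAP 6.4.10, replace the AE-only exception with named reasons: treatment-related AEs, lack of efficacy or worsening of RA, or death. Impute non-response at later treatment-period visits. Align Protocol 3.8.3.6 so that both documents use the same list.
2. Record lack of efficacy or worsening of RA as a discontinuation reason in Protocol 3.4 and the eCRF, with the redirect instruction already given for AEs. This is a category for recording stops that occur, not a new rule on when to stop.
3. For data already collected, classify these stops from the recorded text at the pre-analysis meeting that SAP 4.4 already plans before the randomization code is released.

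Failing every AE stop regardless of relatedness goes beyond both documents and is at most an optional sensitivity analysis.

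The cost is one SAP sentence with a matching protocol edit, one recorded reason and a short blinded review. Response rates in the supportive analysis may fall slightly. Reclassifying *Withdrawal by Subject* may be incomplete, since the underlying reason need not have been documented. The sample size and the primary test are unchanged.
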